8.3 AT-101

During the study period it is the goal to prescribe the fully intended dose of AT-101. It is expected that toxicity of AT-101 can be solved with appropriate measures. However, in case of severe toxicity (grade \geq 3) attributed (possibly, probably or definitively) to AT-101, treatment will be held for a maximum of 8 weeks. If toxicities resolve to \leq grade 1, patients may resume treatment. Patients who are resumed on treatment will be started at a lower dose of AT-101 (25% dose reduction or 30mg BID); if the toxicity recurs (grade \geq 3) then one more dose reduction (50% dose reduction or 20mg BID) will be allowed (upon resolution of toxicity \leq grade 2). If toxicity recurs \geq grade 3, patients will be removed from the study treatment and go to event monitoring.

Note: No dose reduction is allowed in cycle #2 as this is the MTD defining cycle.

| \rightarrow \rightarrow Use the NCI Common Terminology Criteria for Adverse Events (CTCAE) version 4.0 unless | | | | | | | |
|---|--|-----------|--|--|--|--|--|
| otherwise specified $\leftarrow \leftarrow$ | | | | | | | |
| CTCAE System/Organ/Class (SOC) | ADVERSE EVENT | AGENT | ACTION | | | | |
| BASED ON INTERVAL ADVERSE EVENTS (Days 2-3) | | | | | | | |
| Gastrointestinal disorders | BASED ON INTERVAL ≥ Grade 2 Nausea ≥ Grade 2 Vomiting Any Grade Abdominal pain | ADVERSE E | For any of these events that last longer than 48 hours, AT-101 should be omitted and the following actions are recommended: Physical examination, including assessment of vital signs Screening abdominal radiography to include an abdominal series to exclude ileus, small bowel obstruction (SBO), or pneumatosis intestinalis. Consideration for obtaining a CT scan with contrast of the abdomen should be made based on clinical judgment If ileus, non-mechanical SBO, or pneumatosis intestinalis are excluded, AT-101 dosing may be reinstated. If a patient is determined to have ileus, SBO, or pneumatosis intestinalis, AT- | | | | |
| | | | 101 dosing should be permanently discontinued and expectant management with supportive care is recommended, unless clinical signs or symptoms are present that suggest | | | | |
| | | | septicemia or abdominal catastrophe that warrants surgical management. | | | | |

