8.0 Dosage Modification Based on Adverse Events

8.1 Dose Levels (Based on Adverse Events in Tables 8.2 and 8.3)

* Dose level 1 refers to the starting dose.

Omit = The current dose(s) for the specified drug(s) during a cycle is skipped. The patient does not make up the omitted dose(s) at a later time

Hold/Delay = The current dose(s) of all drugs during a cycle is delayed. The patient does make up the delayed dose(s) when the patient meets the protocol criteria to restart drugs.

Discontinue = The specified drug(s) are totally stopped.

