8.2 Lenalidomide

A new course of treatment may begin on the scheduled Day 1 of a new cycle if:

- The ANC is $\geq 1,000/\mu$ L;
- The platelet count is $\geq 25,000/\mu$ L;
- Any lenalidomide-related allergic reaction/hypersensitivity or sinus bradycardia/ other cardiac arrhythmia adverse event that may have occurred has resolved to ≤ grade 1 severity;
- Any other lenalidomide-related adverse event that may have occurred has resolved to \leq grade 2 severity.

If these conditions are not met on Day 1 of a new cycle, the subject will be evaluated weekly and a new cycle of lenalidomide will not be initiated until the toxicity has resolved as described above. If lenalidomide dosing was omitted during the previous cycle and was restarted with a one-level dose reduction without requiring an interruption for the remainder of the cycle, then that reduced dose level will be initiated on Day 1 of the new cycle. If lenalidomide dosing was omitted for the remainder of the previous cycle or if the new cycle is delayed due to toxicity newly encountered on the scheduled Day 1, then the new cycle will be started with a one-level dose reduction.

If either drug is discontinued, patient will come off treatment and go to event monitoring.

| → → Use the NCI Common Terminology Criteria for Adverse Events (CTCAE) version 4.0 unless otherwise specified $\leftarrow \leftarrow$ | | | | |
|---|---|--------------|---|--|
| CTCAE System/Organ/Class (SOC) | ADVERSE EVENT | AGENT | ACTION | |
| | BASED ON INTERVAL | ADVERSE E | EVENTS (Days 2-28) | |
| Investigations | Platelet count decreased*: (Platelets < 10,000/mm ³) | | Omit dose. Follow CBC weekly. If thrombocytopenia resolves to ≤ grade 3 restart lenalidomide at the same dose level. | |
| | | | If thrombocytopenia < 10,000/mm³ recurs, reduce dose by one dose level (5 mg) and continue therapy when platelet count ≥ 25,000/mm³. | |
| | Grade 4 Neutrophil count | | • Omit dose. | |
| | decreased* | | • Follow CBC weekly. | |
| | | Lenalidomide | If neutropenia has resolved to ≤ grade 2, resume dose at same level with GCSF support. | |
| Blood and lymphatic | ≥ Grade 3 Febrile | omi | Omit dose. | |
| system disorders | neutropenia | de | • Follow CBC weekly. | |
| | | | If neutropenia has resolved to ≤ grade 2, resume dose at same level with GCSF support. | |

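### The AT-101 reduction steps in Section 8.3 are reductions only from 40 mg BID: the first step is no change at dose level -1 and an increase at level -2 (secondary: the GI row should name the next pulse)

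*Combined protocol and SAP*

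**What the plan says.** **Dose steps.** The prose of Section 8.3 holds treatment for up to 8 weeks after grade 3 or worse toxicity attributed to AT-101. It then restarts AT-101 at a lower dose, given both as a 25% reduction and as 30 mg BID. If the toxicity recurs, one further step is allowed, given as 50% and as 20 mg BID. A further recurrence ends study treatment.

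Assigned AT-101 doses are not always 40 mg BID. Section 7.21 lists 40 mg BID at levels 1-4, 30 mg BID at level -1 and 20 mg BID at level -2. Section 16.225 sends cohorts to -1 and then -2 if level 1 is too toxic, and Section 7.12 gives phase II patients the phase I MTD. Section 8.1 repeats the level table under a title that begins "Dose Levels (Based on Adverse Events in Tables 8.2 and 8.3". Section 8.2 adds: "If either drug is discontinued, patient will come off treatment and go to event monitoring".

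**GI row.** AT-101 is taken morning and evening on Days 1-3 from cycle 2 (Sections 7.11 and 7.12; Appendix IX). The 8.3 table heading begins "BASED ON INTERVAL ADVERSE EVENTS (Days 2-3" and closes its bracket there. For grade 2 or worse nausea or vomiting, or any abdominal pain, the row says: "For any of these events that last longer than 48 hours, AT-101 should be omitted". It then recommends a work-up. If ileus, non-mechanical small bowel obstruction (SBO) and pneumatosis intestinalis are excluded, "AT-101 dosing may be reinstated"; if one is found, AT-101 stops for good. Section 8.1 defines the action: "Omit = The current dose(s) for the specified drug(s) during a cycle is skipped".

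**The concern.** The milligram figures in 8.3 appear to have been written for a 40 mg BID start and not checked against the two lower levels that the same protocol provides. A patient at level -2 with grade 3 or worse AT-101 toxicity would, on the printed figure, restart at a higher dose. A patient at level -1 would restart at the same dose. Section 8.2 caps lenalidomide at the MTD; Section 8.3 states no such cap for AT-101.

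The GI row matters for a different reason. It is the early screen for ileus and SBO. The Background (clinical safety data with AT-101) names non-mechanical SBO as dose-limiting at 40 mg BID or more on Days 1-3 every other week, typically starting more than 4 weeks after the first AT-101 dose. With 28-day cycles the second pulse is due 4 weeks after the first, so the useful decision is usually about a later pulse, which the row does not mention.

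**Working it through.** **1. Printed steps against each assigned dose.** Inputs: assigned doses from Section 7.21, printed steps from Section 8.3. Change = printed dose / assigned dose - 1.

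| Level | Assigned (BID) | First step, 30 mg | Second step, 20 mg |
|---|---|---|---|
| 1 to 4 | 40 mg | 30/40 - 1 = -25% | 20/40 - 1 = -50% |
| -1 | 30 mg | 30/30 - 1 = 0% | 20/30 - 1 = -33% |
| -2 | 20 mg | 30/20 - 1 = +50% | 20/20 - 1 = 0% |

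The first row reproduces the plan's own 25% and 50%. The other two do not.

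**2. Reading the percentages instead.** Applied to the patient's own dose: 0.75 x 30 = 22.5 mg and 0.50 x 30 = 15 mg at level -1; 0.75 x 20 = 15 mg and 0.50 x 20 = 10 mg at level -2. Section 15.22 gives a single 10 mg tablet strength, so 22.5 and 15 mg cannot be given as equal whole-tablet doses. The 10 mg dose can, but it is not a listed level; nothing below 20 mg BID is.

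**3. How likely the lower levels are.** With true DLT rate p, the chance that a level passes is e = (1-p)^3 + 3p(1-p)^5. This gives 0.906, 0.709, 0.494, 0.309 and 0.172 for p = 10% to 50%, matching the table in Section 16.227. The chance that level 1 fails is f = 1 - e. The chance that -1 or -2 then passes, assuming the same p at all three levels, is f(e + fe).

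| True DLT rate | Level 1 fails | MTD is -1 or -2 |
|---|---|---|
| 10% | 0.09 | 0.09 |
| 20% | 0.29 | 0.27 |
| 30% | 0.51 | 0.38 |
| 40% | 0.69 | 0.36 |
| 50% | 0.83 | 0.26 |

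These are first-pass figures; they ignore patients added later to bring a level to six. The true DLT rate is not known from the documents. The low end is plausible: the Background gives 40 mg BID for 3 days every 21 days as a recommended phase 2 dose, and level 1 carries the lowest lenalidomide dose.

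**4. GI timing.** There are 3 days x 2 doses = 6 AT-101 doses per cycle, the last on the evening of Day 3.

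- Onset on Day 2 reaches 48 hours on Day 4, and onset on Day 3 reaches it on Day 5. Either way 0 of 6 doses remain, whatever the clock times.
- Onset on Day 1 after the first dose leaves at most 1 of 6 (the Day 3 evening dose), assuming 12-hour spacing.

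**The case against.** **On the steps.** Section 8.3 itself requires a lower restart dose, so raising a patient from 20 to 30 mg BID would break the sentence that contains the figure. Section 8.1 lists 40, 30 and 20 mg BID as levels for adverse events in 8.3, which makes 20 mg BID the natural step from level -1. Section 16.225 also allows the study team to re-evaluate the regimen once the lower levels are in use. All of this makes a wrong dose less likely. It does not correct the figures: 8.3 does not refer to the 8.1 table, the re-evaluation is optional, and no step exists below 20 mg BID.

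**On the GI row.** A reader might infer that nothing stops the next Day 1 doses when grade 2 nausea or vomiting, or low-grade abdominal pain, persists or has not been worked up. The 8.3 hold starts only at grade 3, and the new-cycle criteria in 8.2 concern lenalidomide ("Any other lenalidomide-related adverse event that may have occurred has resolved to" grade 2 or less). The documents do not support that inference, because the row makes reinstatement conditional on excluding ileus, SBO and pneumatosis. When no dose is left in the cycle, reinstatement can only mean the next pulse. A symptom still present on the next Day 1 has also lasted more than 48 hours, so those doses become the current ones to skip. What stands is that the row leaves this to be worked out, and that its heading can be read as limiting either the day of onset or the day of action.

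**On frequency.** The dose-limiting SBO was seen with a pulse every other week; this trial gives one pulse per 28-day cycle. The Background reports one case in about 200 patients on 40 mg BID for 3 days every 21 days with docetaxel. Few patients may meet the problem.

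**Conclusion.** The dose-step error is real and follows from the protocol's own tables. The printed milligram steps are correct at levels 1-4, give 0% then -33% at level -1, and give +50% then 0% at level -2. It has consequences only if phase I de-escalates below level 1 and a patient there resumes after grade 3 or worse AT-101 toxicity. The first-pass chance that level 1 fails is 0.09 to 0.83 over assumed true DLT rates of 10-50%. It would be wrong to read this as a prediction that patients will be given more drug after toxicity, since the accompanying words forbid it; the defect is that the words and the figure conflict.

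The GI row is workable and needs only a clarification for onset on Day 2 or 3. Both points concern operability and sit at the low end of minor. No alpha, power or sample-size figure changes.

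**What to change.** **Section 8.3, prose.** Replace the two percentage-and-milligram steps with: *one step down the 40/30/20 mg BID ladder in 8.1 from the patient's current AT-101 dose; a patient already at 20 mg BID discontinues AT-101 and, per 8.2, comes off treatment.* Levels 1-4 keep exactly their present steps. Level -1 has one step and level -2 has none, which the team should accept knowingly.

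**Section 8.3, GI row.** Add: *If no AT-101 dose remains in the cycle, the next cycle's Day 1-3 AT-101 doses are omitted (not made up; lenalidomide continues per 8.2) unless ileus, SBO and pneumatosis intestinalis have been excluded.* This chooses Omit rather than Hold/Delay. Under 8.1, Hold/Delay would postpone both drugs and make the doses up later.

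**Cost.** Two sentences in an amendment, with no added visits and no tests beyond those the row already names. The downside is an occasional missed AT-101 pulse when the work-up is not complete by the next Day 1.

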9.0 Ancillary Treatment/Supportive Care

- 9.1 Antiemetics may be used at the discretion of the attending physician.
- 9.2 Blood products and growth factors should be utilized as clinically warranted and following institutional policies and recommendations. Growth factors cannot be used during Cycle 2 of the Phase I portion due to DLT monitoring. The use of growth factors should follow published guidelines of the American Society of Clinical Oncology (42) Update of Recommendations for the Use of Hematopoietic Colony-Stimulating Factors: Evidence-Based, Clinical Practice Guidelines. J Clin Oncol 18(20): 3558-3585, 2000.
- 9.3 Patients should receive full supportive care, including transfusions of blood and blood products, antibiotics, and antiemetics when appropriate. Any blood transfusions administered must be irradiated blood products to reduce risk of transfusion mediated graft versus host disease in CLL patients receiving T-cell suppressive therapy. Leukocyte reduction of all blood products for patients on protocol is also required. All blood products and concomitant medications such as antidiarrheals, analgesics, and/or antiemetics received from the first day of study treatment administration until 30 days after the final dose will be recorded in the medical records.
- 9.4 Diarrhea: This could be managed conservatively with loperamide. The recommended dose of loperamide is 4 mg at first onset, followed by 2 mg every 2-4 hours until diarrhea free (maximum 16 mg/day).

In the event of grade 3 or 4 diarrhea, the following supportive measures are allowed: hydration, octreotide, and antidiarrheals.

If diarrhea is severe (requiring intravenous rehydration) and/or associated with fever or severe neutropenia (grade 3 or 4), broad-spectrum antibiotics must be prescribed. Patients with severe diarrhea or any diarrhea associated with severe nausea or vomiting **should be hospitalized** for intravenous hydration and correction of electrolyte imbalances.

9.5 Tumor Lysis Syndrome (TLS) Prophylaxis and Treatment

Subjects **must receive** Allopurinol 300 mg/day (or an equivalent standard agent for prevention of hyperuricemia) orally for the first two weeks of the first cycle of protocol therapy. Allopurinol may be continued after the first two weeks at the investigator's discretion and as clinically indicated. Subjects should be observed closely for signs and symptoms of TLS during the initial cycle of therapy. Subjects should be encouraged to drink an abundant amount of fluid prior to treatment. Subjects should maintain adequate hydration and urine output.

9.6 **Tumor Flare Reaction (TFR)**

Patients may not receive any prophylaxis for TFR. We do not anticipate severe (grade 4) TFR. It is to be noted that in our previous clinical trial (using 25mg PO QD) no grade 4 TFR was observed. Also, as occurrence of the TFR can positively impact response and progression free survival (PFS) (Chanan-Khan et al *Cancer 117(10) 2127-35*), steroid prophylaxis for TFR will not be used. We recommend the following management plan for TFR:

Grade 1-2 TFR: Grade 1 defined as mild pain not interfering with function; grade 2 defined as moderate pain; pain or analgesics interfering with function, but not interfering with activities of daily living (ADL). Patients can be treated with (a) non-steroidal anti-inflammatory agents (preferred agent - ibuprofen 400-600mg PO Q8 hours) to decrease inflammatory response and / or (b) morphine sulphate (or equivalent analgesic) to control flare associated pain.

Grade 3 TFR: Defined as severe pain; pain or analgesics interfering with function and interfering with ADL. Patients will be treated with (a) non-steroidal anti-inflammatory agents (preferred agent - ibuprofen 400-600mg PO Q8 hours) to decrease inflammatory response and (b) morphine sulphate (or equivalent analgesic) to control flare associated pain. Also, (c) low-dose steroid treatment (preferred agent prednisone 20mg PO QD x 7 days and then 10mg PO QD x 7 days) can be added to this regimen at treating physician's discretion and as clinically indicated.

Grade 4 TFR: Defined as disabling. (a) treatment will be stopped until TFR grade is \leq grade 1. (b) steroid treatment will be initiated (preferred agent prednisone 20mg PO QD x 7 days and then 10mg PO QD x 7 days) can be added to this regimen at treating physician's discretion and as clinically indicated. High dose steroid (Prednisone 60-100mg PO QD x 5 days and then tapering doses, alternatively medrol pack can be used) maybe initiated as clinically indicated and at treating physician's discretion. (c) non-steroidal anti-inflammatory agents (preferred agent - ibuprofen 400-600mg PO Q8 hours) to decrease inflammatory response and morphine sulphate (or equivalent analgesic) to control flare associated pain may be added at treating physician's discretion.

9.7 Lymphadenitis (cytokine release syndrome)

Some subjects with CLL have experienced lymphadenitis characterized by swelling of the lymph nodes, fever, and pain. This syndrome is likely a result of cytokine release. If these symptoms occur, subjects should be treated with methylprednisolone 50 mg IV or dexamethasone 10 mg IV (or equivalent dose of corticosteroid therapy, either IV or PO) at least once daily until symptoms resolve.

9.8 **Anticoagulation prophylaxis:** Due to high-risk of thromboembolism with lenalidomide all subjects will receive thromboprophylaxis either with:

(a) warfarin 1 mg (for <70 kg body weight) and 2 mg (\geq 70 kg body weight) orally QD while on lenalidomide therapy either alone or in combination phase. Full anticoagulation may be done if in investigators' assessment there is a higher risk of developing a venous thromboembolic event. Warfarin should be stopped if platelet count is \leq 50,000 and should be resumed once platelet counts increase and are above \geq 50,000. Patients who are on full therapeutic dose of warfarin or low-molecular heparin for prior episode of DVT or other indications can be enrolled and treated on this protocol but will not require low-dose warfarin prophylaxis. Patients developing a DVT/PE while on this study should have their treatment held and receive full therapeutic anticoagulation either with warfarin (target INR 2-3) or low-molecular weight heparin as per standard clinical practice. Once therapeutic level of anticoagulation is achieved, these patients can resume therapy on the study. Anticoagulation in these patients should be continued throughout the duration of therapy and can be stopped 1 week after the last dose of lenalidomide.

(b) Low-dose aspirin (81 mg PO QD) can be used as an alternative strategy.

Selection of either (a) vs. (b) will be at the treating physician's discretion.

- 9.9a Contraindicated medications: Patient should not be allowed to take concurrent oral iron supplements (including nutritional supplements containing iron) while taking AT-101.
- 9.9b Pneumocystis jiroveci prophylaxis: Co-trimoxazole (Bactrim®) SS, 1 tablet by mouth daily beginning Day 1 and continued for the duration of treatment until one month following completion of treatment. Co-trimoxazole intolerant patients will receive dapsone 100 mg per day by mouth or atovaquone 1,500 mg per day by mouth for the same period.
- 9.9c Herpes Simplex and Herpes Zoster prophylaxis: Acyclovir 400 mg by mouth twice a day OR valacyclovir 500 mg by mouth daily beginning Day 1 and continued for the duration of treatment until one month following completion of treatment. Substitution with comparable doses of famciclovir is allowed for the same period.

10.0 Adverse Event (AE) Reporting and Monitoring

10.1 Adverse Event Characteristics

CTCAE term (AE description) and grade: The descriptions and grading scales found in the revised NCI Common Terminology Criteria for Adverse Events (CTCAE) version 4.0 will be utilized for AE reporting. All appropriate treatment areas should have access to a copy of the CTCAE version 4.0. A copy of the CTCAE version 4.0 can be downloaded from the CTEP web: (http://ctep.cancer.gov/protocolDevelopment/electronic applications/ctc.htm)

10.11 Adverse event monitoring and reporting is a routine part of every clinical trial. First, identify and grade the severity of the event using the CTCAE version 4.0. Next, determine whether the event is expected or unexpected (see Section 10.2) and if the adverse event is related to the medical treatment or procedure (see

Section 10.5). With this information, determine whether the event must be reported as an expedited report (see Section 10.). Expedited reports are to be completed within the timeframes and via the mechanisms specified in Sections 10.4. All AEs reported via expedited mechanisms must also be reported via the routine data reporting mechanisms defined by the protocol (see Sections 10.6 and 18.0).

10.12 Each CTCAE term in the current version is a unique representation of a specific event used for medical documentation and scientific analysis and is a single MedDRA Lowest Level Term (LLT). Grade is an essential element of the Guidelines and, in general, relates to **severity** for the purposes of regulatory reporting to NCI.

NOTE: A severe AE, as defined by the above grading scale, is NOT the same as serious AE which is defined in the table in Section 10.4.

10.2 Expected vs. Unexpected Events

- The determination of whether an AE is expected is based on agent-specific information provided in Section 15.0 of the protocol and the study specific consent form.
- Unexpected AEs are those not listed in the agent-specific information provided in Section 15.0 of the protocol and the study specific consent form.

NOTE: "Unexpected adverse experiences" means any adverse experience that is neither identified in nature, severity, or frequency of risk in the information provided for IRB review nor mentioned in the consent form.

10.3 Assessment of Attribution

When assessing whether an adverse event is related to a medical treatment or procedure, the following attribution categories are utilized:

Definite - The adverse event *is clearly related* to the agent(s). Probable - The adverse event *is likely related* to the agent(s). Possible - The adverse event *may be related* to the agent(s). Unlikely - The adverse event *is doubtfully related* to the agent(s). Unrelated - The adverse event *is clearly NOT related* to the agent(s).

Events determined to be possibly, probably or definitely attributed to a medical treatment suggest there is evidence to indicate a causal relationship between the drug and the adverse event.

